4.5 Exclusion Criteria

Never used the drug;

Serious violation from the study protocol judged by investigator and/or sponsor;

All the subjects with at least one medication record should be included in the ITT set. Reasons for exclusion should be described and the CRF/eCRF should be maintained for further check.

4.6 End of Trial

End of the whole trial is defined as 9 months after enrollment of the last patient.

There are a few situations for end of trial for each subject as below:

- 1 Death
- 2 The subject or his/her legal representative requests to withdraw from the study and refuses to be followed up.
- 3 The subject is lost to to follow-up
- 4 End of the whole trial

The database will be locked after the end of the whole trial. For subjects who have not reached PFS event, the sponsor will continue to provide the product if they are willing to continue the administration after investigator's evaluation, and they will be followed up in accordance with the original schedule for treatment period (including safety evaluation, tumor assessment, drug counting) until progression of disease, death or loss of follow-up, or voluntary withdrawal from the trial. The sponsor is responsible for paying the cost for safety evaluation and tumor assessment but not for collection of data. If any SAE occurs during treatment, one SAE form needs to be filled in by investigators and reported to the sponsor. Survival of all the subjects will not be followed up after the end of the whole trial.

5 Treatment

5.1 Dosage and administration regimen of study drug

Randomized comparison part:

All the subjects will be randomized (1: 1) into Fruquintinib group A (4mg qd daily) and group B (5 mg qd 3-week on/1-week off).

Both of the groups will receive the treatment in a cycle of 4 weeks, until progression of disease, unacceptable toxicity or withdrawal of the informed consent.

Expansion part:

According to the preliminary results of the randomized comparison part, the administration method and recommended dose for phase II/III studies are determined as group B (5 mg qd 3-week on/1-week off) for the expansion part, using 4 weeks as one therapeutic cycle as well, until progression of disease, unacceptable toxicity or withdrawal of informed consent.

5.2 Source, strength and shelf-life of the product

Fruquintinib is provided by Hutchison Medi Pharma (Shanghai) Co., Ltd. Hutchison Medi Pharma (Shanghai) Co., Ltd. sub-contracted Yiling Pharmaceutical Co., Ltd for production and packaging, and performed technical guidance and quality control by itself.

Product Name	Form	Strength	Administration method	Batch No.	Shelf-life
Fruquintinib	Capsules	1.0mg	p.o.	120602	2 years
Fruquintinib	Capsules	1.0mg	p.o.	120901	2 years
Fruquintinib	Capsules	5.0mg	p.o.	120603	2 years
Fruquintinib	Capsules	1.0mg	p.o.	1309051	2 years
Fruquintinib	Capsules	5.0mg	p.o.	1309061	2 years

5.3 Product Labeling

Fruquintinib is provided as the form of capsule in a bottle and maintained at the study site after meeting the acceptance criteria by the user. The study nurse is responsible for storage, maintenance, dispensation and counting of the study drug. The sponsor will recover the remaining study drug after the end of study.

Information in the package labelling of the study drug contains the following: study No., storage conditions, contents, dosage, administration method, batch number, shelf-life and standard text "only for clinical studies" and "kept away from reach of children".

5.4 Drug storage

All of the study drugs must be stored according to specifications, and placed in a safe and sealed place under room temperature or in a shade place.

The storage temperature needs to be noted and kept in appropriate document.

The study drug is only for study and limited to the content specified in this protocol.

5.5 Grouping method and drug dispensation

The investigator or study nurse will dispense the study drug as required. The investigator should fill in the Summary Sheet of Drug Dispensation promptly and accurately at the

dispension.

5.6 Dosage and administration method

Randomized comparison part:

Group A: dose of Fruquintinib: 4mg qd po (under fasting state), daily.

Group B: dose of Fruquintinib: 5mg qd po (under fasting state), 3-week on/1-week off.

Expansion part: group B is selected for this part in accordance with the results from the randomized comparison part.

5.7 Administration method

It is taken orally with 200ml warm water. The accurate time of actual medication should be recorded each time. Fasting administration is preferred, i.e., 1 hour prior to breakfast or 2 hours after that. Subjects who could not tolerate fasting administration due to gastrointestinal reaction can change to postprandial administration after evaluation by investigators.

Every effort should be made to ensure subject's compliance with the study protocol during the study. The missed dose could be made up before 10pm on that day when the subject misses his/her dose in the morning. However, if the subject misses the scheduled dose and fails to make up the dose on that day, he/she must take the next dose as specified, however, the missed dose is not required to make up. The missed dose must be reported to investigators and recorded on CRF/eCRF. If vomiting occurs within 30 minutes after administration, the administration could be resumed.

Strenuous exercise should be avoided during the trial; use of alcohol, smoking or beverage containing caffeine are forbidden. Intake of grapefruit, shaddock or beverage containing the above fruits should be avoided during the trial.

5.8 Accountability

Registration and record of the study drug need to be managed by designated person. The study site should establish one set of systemic processing and operational procedure as to ensure the receipt of the study drug by one designated person, accurate record of drug dispensation, proper use and storage of the study drug.

- ◆ Drug registration form; ① type of study drug received from the sponsor; ② dosage form and dose; ③ batch number and shelf-life; ④ dosage form, dose, numbers and date of drug delivery (signed by both parties) sent to the investigators.
- ◆ The investigators should provide the registration form of the study drug: to register the subject's name, package number, time of medication, administration and dosage, signature by the person who administered the drug, and recycle the package.
- ◆ Subject's medication, lost and missing dose as well as misuse should be recorded carefully.

- ◆ Unused drugs should be stored in accordance with the requirement for storage, and the stored drugs should be inspected if it is in accordance with the requirement by designated person on a regular basis.
- ◆ The recovery, registration and record of the remaining drugs should be well performed after the completion of the trial, and the study drugs should be disposed in accordance with GCP requirement.

5.9 Principle and method for management of toxic and side effects after administration

5.9.1 Principle on management of toxic and side effects during the study

If relevant toxic and side effects occur during the study, the management of toxic and side effects, dose interruption and dose reduction need to follow the following principles. Management of the toxic and side effects that are possibly related with Fruquintinib is provided in 5.9.2.

- When grade 4 hematological toxicity or grade 3 non-hematological toxicity and relevant toxic and side effects listed in Table 7 occur, the dose of Fruquintinib should be interrupted, and could be resumed or reduced to the next lower dose if the toxicity could be recovered to grade 1 or below within 14 days; the medication needs to be permanently discontinued if it could not be recovered within 14 days.
- Symptomatic management and treatment could be given actively for controllable nausea, vomiting, asthenia, diarrhea, hypertension, pain, fever with defined cause (eg., infection or tumor) and elevation of alkaline phosphatase in non-hematological toxicity, rather than dose interruption or dose reduction;
- When several AEs occur simultaneously, the dose should be adjusted according to the most severe AE;
- It is inappropriate to discontinue this category of drug for too long, in principle the dose could be resumed when the toxicity is relieved to grade 1;
- Dose adjustment could be performed at any time according to intolerable toxicity in each cycle of administration. The dose must not be uptitrated to its previous level after reduction; 2 dose adjustments are allowed at most (ie., 5mg 3/1 could be downtitrated to 4mg 3/1 for the first adjustment and 3mg 3/1 for the second adjustment; 4mg QD could be downtitrated to 3mg QD for the first adjustment and 2mg QD for the second adjustment)); dose adjustment is not allowed but dose interruption is allowed after the dose is adjusted to 3mg 3/1 or 2mg QD.

5.9.2 Management of the expected adverse events of Fruquintinib

If the toxic and side effect is judged by the investigator to be possibly related with Fruquintinib, management of the effect needs to comply with the principle in Section 5.9.1 and relevant interventions should be given. The phase I tolerability test showed the adverse reactions related with Fruquintinib mainly included hypertension, proteinuria, hand-foot

syndrome, diarrhea, stomatitis and hypothyroidism or elevated TSH.

Management of acute hypertension

Management of mild-to-moderate hypertension in accordance with the following procedure:

1. No treatment is required for asymptomatic transient (<24 hours) increase of diastolic pressure >20mmHg or >150/100mmHg (previously normal range), and study drug is continued.
2. One or more antihypertensive agents could be added for recurrent or persistent (>24 hours) increase of diastolic pressure >20mmHg or >150/100mmHg (previously normal range) or symptoms. Use of the study drug is continued while blood pressure is monitored.
3. If the blood pressure keeps >160/100mmHg for more than one week (previously normal range) after antihypertensive therapy, interruption of Fruquintinib is considered with continuation of antihypertensive therapy and close monitoring. If the hypertension could be recovered to grade 1-2 within 14 days, reuse of Fruquintinib is decided by the investigator together with the sponsor (use of antihypertensive agent will be continued).
4. If the blood pressure increases to >160/100mmHg after the dose of Fruquintinib is resumed, it is decided by the investigator and the sponsor whether to downtitrate the dose of Fruquintinib to the next level.
5. If the blood pressure still increases to >160/100mmHg and lasts for more than one week at the dose level lower than the previous one when in combination with concomitant antihypertensive agent, the study drug should be terminated.

Principle on treatment with mild-to-moderate antihypertensive agent:

- Fruquintinib might lead to elevation of blood pressure;
- Calcium channel antagonist is the preferred drug, and β -receptor blocker is the 2nd choice when use of calcium channel antagonist is contraindicated;
- Angiotensin converting enzyme inhibitor and angiotensin II receptor blocker are mainly used for treatment of hypertension combined with proteinuria
- If the blood pressure is >140/90mmHg after treatment, the dose of drug could be considered to increase to adequate dose and administered in combination with selective β -receptor blocker, thiazide diuretics, angiotensin converting enzyme inhibitor and angiotensin II receptor blocker as required. If the blood pressure is still >140/90mmHg after 24 hours, the dose of combined drug could be considered to increase to adequate dose, or combined with the 3rd antihypertensive agent;

Principle on management of severe hypertension in accordance with the following procedure:

When the diastolic pressure increases to ≥ 110 mmHg or the systolic pressure increases to ≥ 180 mmHg, the management is performed in the following procedure:

1. Interruption of the study drug and hospitalization;
2. Two antihypertensive agents combined therapy (including one dihydropyridine calcium channel blocker), or adjustment of the antihypertensive agent previously used;
3. Intravenous antihypertensive therapy whilst oral therapy when target organ impairment occurs;
4. Stabilization of the blood pressure, even rescue through request to relevant experts and personnel;
5. When the blood pressure decreases to $< 140/90$ mmHg, reuse of the study drug is considered, refer to the aforementioned step 4.

Management of proteinuria

If urine protein 2+ is found in consecutive two urinalyses during the treatment, please collect 24-hour urine. If the urinalysis or 24-hour urine protein quantification is graded as NCI CTC-AE 1, keep close observation; keep close observation for grade 2 and 24-hour urine protein quantification < 2 g; interrupt the dose for 24-hour urine protein quantification ≥ 2 g, and reduce the dose if it could be recovered to grade 1 or below within 2 weeks; if the urianlysis or 24-hour urine protein quantification is graded as NCI CTC-AE 4 (nephrotic syndrome), discontinue the study drug permanently.

Management of hand-foot syndrome

If the subject develops ≤ 2 grade hand-foot syndrome, symptomatic treatment could be given. Avoid friction, pressure and contact with heat objects of hands and feet. Keep the skin of hands and feet moist or use urea cream or lanolin cream-containing lotion appropriately, which will be helpful for relieving the symptom and healing of the lesion. Patients with serious symptoms (in particular those with pain) could use ointment for relieving burning and pain or oral voltaren appropriately, which will be helpful for relieving the symptoms.

For subjects with grade 3 or above hand-foot syndrome (serious cutaneous reactions, including exfoliation, blister, hemorrhage, edema with pain, affecting daily life), please interrupt the dose in accordance with the principle in Section 5.9.1. The dose could be resumed or reduced if the toxicity could be recovered to grade 1 or below within 14 days.

Diarrhea

If the subject develops grade 1-2 diarrhea, close observation or use of drugs for improving intestinal function could be given; if grade 3 diarrhea occurs, Imodium or other drugs for improving intestinal function could be given, the toxicity could be recovered generally within 3 days and the dose could be continued; dose interruption is required if it lasts for more than 3 days.

Mucositis oral

If the subject develops grade 1-2 stomatitis (including oral ulcer, mucositis, gingivitis, laryngeal discomfort, angular stomatitis), local antibiotics (including those for anaerobic bacteria) and antifungal drugs, mucosa protective agent and local anesthetics, as well as oral Xiguashuang spray and Yinhuangjiedu tablet could be given, and the administration could be continued. Use of iodine-containing product and long-term use of hydrogen peroxide should be avoided; soft and non-irritable food is proposed in terms of diet, and spicy, acid or irritable food should be avoided. If the patient could not swallow food or liquid diet, parenteral fluid or nutritional support might be needed.

If the stomatitis could not be recovered and affects food intake and body weight after treatment, the dose needs to be interrupted; if it could be recovered to grade 1 within 14 days, continuation of the administration with the original dose or dose reduction could be considered.

Hypothyroidism and elevated TSH

If the subject develops clinically significant hypothyroidism (with or without clinical symptoms), or the TSH keeps increasing with clinical symptoms (with or without decreased T4), he/she is advised to receive hormone replacement therapy.

Platelet count decreased

If the subject develops grade 2-3 thrombocytopenia ($<75 \times 10^9/L$), he/she is advised to interrupt the dose, and receive recombinant human interleukin -11 for injection for platelet-increasing therapy; apheresis platelets could be transfused when grade 4 toxicity occurs.

For the management of other toxic and side effects, the subject's benefit should be sufficiently considered and proper management and treatment are provided under the above principle on management of toxic reactions.

5.9.3 Provisions on dose adjustment resulted from toxicity:

When drug related toxicity occurs, the treatment of Fruquintinib needs to be performed in accordance with the procedure in Table 7.

Table 7 Provisions on dose adjustment resulted from drug related toxicity

Type of AE and CTCAE grade	Measures	Regimen for dose reduction
Study drug related adverse events		
● Neutropenia CTCAE grade 3 ($<1 \times 10^9/L$)	dose interruption until recovery to \leq CTCAE grade 1 or baseline;	administration method of 3-week on/1-week off: downtitrated to
● Thrombocytopenia CTCAE grade 2 ($<75 \times 10^9/L$)	resume the administration with the reduced dose in accordance with the protocol;	4 mg for the first adjustment; to 3 mg for the second adjustment in 5mg dose group;
● Hand-foot syndrome CTCAE grade 3, affecting walking and joint movement	If the patient could not be recovered to	or: administration method of

Type of AE and CTCAE grade	Measures	Regimen for dose reduction
● Hypertension CTCAE grade 3, still persisting for more than 48 hours after pharmacotherapy	≤CTCAE grade 1 or baseline within 14 days, the study drug must be permanently discontinued.	once daily for consecutive administration: downtitrated to 3 mg for the first adjustment; to 2 mg for the second adjustment in 4mg dose group. If the dose after the second adjustment could not be tolerated, the study drug must be discontinued regardless of the administration method.
● Stomatitis; CTCAE grade 2, still persisting for 3 days or more and intolerable after pharmacotherapy		
● Proteinuria; CTCAE grade 2 (≥2.0g/24-hour quantification)		
● Liver injury; total bilirubin >2×ULN and /or aminotransferase >3×ULN in patients with normal baseline;		
● Diarrhoea; CTCAE grade 3, still persisting for 3 days or more after proper antidiarrheal and symptomatic treatment		
● Any drug-related AE≥TCTAE grade 3		

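### Sections 5.9.1, 5.9.2 (with 4.4) and Table 7 contradict each other on dose interruption, resumption and stopping, and two of the three conflicts can change who counts as an event in primary tolerability variables

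*Protocol*

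**What the plan says.** **Resumption.** Section 5.9.1 states that an interrupted dose "could be resumed or reduced to the next lower dose if the toxicity could be recovered to grade 1 or below within 14 days". Section 5.9.2 repeats the option for hand-foot syndrome ("The dose could be resumed or reduced if the toxicity could be recovered to grade 1 or below within 14 days"). For stomatitis that has recovered it says "continuation of the administration with the original dose or dose reduction could be considered". Table 7 in Section 5.9.3 covers both toxicities and gives one instruction: "resume the administration with the reduced dose in accordance with the protocol".

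**Persistent hypertension.** The Table 7 row reads "Hypertension CTCAE grade 3, still persisting for more than 48 hours after pharmacotherapy", and its measure is interruption. If recovery to grade 1 or below, or to baseline, is not reached within 14 days, the drug must be stopped permanently; Section 4.4 has the same criterion. Section 5.9.2, under mild-to-moderate hypertension, reads "If the blood pressure keeps >160/100mmHg for more than one week (previously normal range) after antihypertensive therapy, interruption of Fruquintinib is considered" and then "If the hypertension could be recovered to grade 1-2 within 14 days, reuse of Fruquintinib is decided by the investigator together with the sponsor".

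**Controllable events.** For controllable nausea, vomiting, asthenia, diarrhea, hypertension, pain, fever of known cause and raised alkaline phosphatase, Section 5.9.1 provides symptomatic treatment "rather than dose interruption or dose reduction", with no upper grade. The last row of Table 7 covers every drug-related event of grade 3 or above, with no exemption.

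**Endpoints.** Section 8.1 lists, among the primary variables, adverse events leading to permanent discontinuation and those leading to interruption or reduced dose (one combined item). Section 8.2.2 compares both between the randomized groups by CMH chi-square test.

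**The concern.** These tolerability variables record actions that the protocol itself prescribes. If two passages prescribe different actions for the same toxicity, the variable depends partly on which passage the site followed. Nothing in the text settles the order: 5.9.2 says management must comply with 5.9.1, and 5.9.3 says treatment must follow Table 7. The trial is open-label, so whoever chooses the passage knows the patient's arm. Patient handling is also at stake: the same persistent hypertension can lead to continued dosing, an interruption or a mandatory stop. The same text governs the expansion part, whose primary endpoints include tolerability.

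**Working it through.** The protocol states no figure on this point, so there is none to reproduce. The check follows typical cases through each passage and asks whether a Section 8.1 variable changes.

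| Case | Table 7 (and 4.4) | 5.9.1 / 5.9.2 | Variable that changes |
|---|---|---|---|
| (a) Grade 3 hand-foot syndrome, recovered to grade 1 within 14 days | Interrupt, resume at reduced dose | Interrupt, resume at same or reduced dose | Neither primary variable; only reduction taken alone |
| (b1) Drug-related grade 3 hypertension lasting between 48 hours and one week on therapy | Interrupt | Continue; one-week point not reached | Interruption/reduced dose |
| (b2) Hypertension, drug interrupted, grade 2 at day 14, baseline lower | Permanent stop | Reuse may be decided by investigator and sponsor | Permanent discontinuation |
| (c) Drug-related grade 3 asthenia, nausea, vomiting or pain, controllable | Interrupt (last row) | Symptomatic treatment, no interruption | Interruption/reduced dose |

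On (b), Table 7 uses a CTCAE grade and 5.9.2 uses mmHg. The protocol shows that they overlap: 5.9.2 speaks of recovery to grade 1-2 from the state above 160/100 mmHg, which places that state above grade 2.

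**Size, from the interim results in Section 3.1.2**

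- Hypertension of grade 3 or above: 22.5% × 40 = 9 patients. No split by arm, duration on therapy or day-14 grade is given.
- Hand-foot syndrome of grade 3 or above: 17.5% × 40 = 7 = 6 + 1, that is 6/20 = 30% on 4 mg daily and 1/20 = 5% on 5 mg 3/1. Sections 5.9.1 and 5.9.2 and Table 7 all interrupt at grade 3, so the rules give the combined variable 6/20 vs 1/20 from these cases whichever passage is followed.
- Permanent discontinuation for toxicity: 7/20 = 35% vs 4/20 = 20%, a difference of 15 points. One patient is 1/20 = 5 points.

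To show how much one reclassified patient matters, I used the uncorrected Pearson chi-square as a stand-in for the CMH test:

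| Discontinued, 4 mg daily vs 5 mg 3/1 | Difference | Chi-square p | Fisher p |
|---|---|---|---|
| 7 vs 4 (reported) | 15 points | 0.288 | 0.480 |
| 8 vs 4 | 20 points | 0.168 | 0.301 |
| 7 vs 3 | 20 points | 0.144 | 0.273 |
| 6 vs 4 | 10 points | 0.465 | 0.716 |
| 7 vs 5 | 10 points | 0.490 | 0.731 |

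One patient moves the estimated difference by a third of its size (5 of 15 points). It does not take either p-value across 0.05. Only the first row is reported data; the others are hypothetical.

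**Lesser mismatches.** For diarrhea, 5.9.2 interrupts after more than 3 days and Table 7 at 3 days or more. At the lowest dose level, 5.9.1 still allows interruption, while Table 7 requires stopping if that dose is not tolerated. The text on proteinuria agrees, and the 14-day limit is common to 4.4, 5.9.1 and Table 7.

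**The case against.** Four points on the other side have weight.

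1. **The last row of Table 7 can be read as residual.** On that reading it covers only toxicities without a row of their own, and the hypertension and diarrhea rows, which require persistence after treatment, fit the exemption for controllable events. This narrows conflict (c) but does not remove it: asthenia, nausea, vomiting and pain have no row, so the residual row applies to them and the exemption in 5.9.1 contradicts it.
2. **The one-week rule sits under mild-to-moderate hypertension.** Severe hypertension (systolic at least 180 or diastolic at least 110 mmHg) has its own procedure, which does interrupt. Conflict (b) is therefore confined to pressures above 160/100 mmHg and below the severe thresholds.
3. **Both arms share the same text.** Rule choice may mainly add noise. The protocol shows no differential handling; open-label treatment makes it possible, no more.
4. **The regimen was not chosen on interruptions or reductions.** The interim conclusion cites grade 3 or above events, grade 3 hand-foot syndrome, serious events, permanent discontinuation and efficacy. Of these, only permanent discontinuation is touched directly, through (b2).

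A reader might infer that the 25-point difference in hand-foot syndrome (30% vs 5%) could appear or vanish as a primary result depending on the passage followed. The documents do not support this, because every passage interrupts. Only reduction taken alone could range from 0/20 vs 0/20 to 6/20 vs 1/20, and the upper end assumes that all seven patients recovered in time to restart, which is not reported. Nor can the 17/20 vs 8/20 patients with grade 3 or above events be treated as dose reductions; the protocol reports no reduction counts.

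**Conclusion.** The contradictions are in the current text and should be fixed. Conflicts (b) and (c) can change whether a patient counts under a primary tolerability variable; conflict (a) changes only the reduction rate taken alone. How many patients are affected cannot be determined from the protocol: the nine grade 3 or above hypertension cases are a pool in which (b) could arise, not a count of misclassified patients. Each affected patient shifts an arm's rate by 5 points. This rests on Section 8.1 as the list of primary variables. The synopsis is not uniform: its statistical section names interruption and discontinuation but not reduction, and its assessment section places discontinuation and reduction under tolerability, outside the primary safety endpoints. A reader might also infer that the interim choice of regimen is unsound on this ground; the documents do not show that. This review takes no view on which clinical rule is right.

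**What to change.** The passages must be reconciled by the clinical team: one trigger, one recovery threshold and one resumption rule for each toxicity, consistent across 4.4, 5.9.1, 5.9.2 and Table 7, with a sentence saying which passage governs if they differ. The amended text should apply to patients still on treatment and to the expansion part.

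For events already recorded, list each interruption, reduction and permanent discontinuation with the passage it followed, and report the three outcomes separately by arm. This is a sensitivity description only. It cannot repair the completed interim comparison, and an action can be called mandated or discretionary only against a named passage.

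The cost is amendment wording, a memo to the two sites, and a patient-level review of dose actions. That review needs drug-relatedness, duration after start of treatment and the grade at day 14, so it is more than one derived variable, but it covers only 40 randomized and about 20 expansion patients.
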